1.2. Schema

Figure 1. Schema of the assessment study

1.3. Schedule of Activities (SoA) - see more details in Section 4.

						Inte	rventi	ion Pe	riod V	Veeks (w	ith a wash	out of	16 to	18 mo	nths)					Notes
				Gener	ation	1				Rescreen										
Procedure	before W1)	W1 D1 V1	W1	W1 D5	W2 D1 V2	W2	W2 D5 V3	W3	W4 V4	Develop G2	(< 15 d before W1)	W1 D1 V1	W1	W1 D5	W2 D1 V2	W2	W2 D5 V3	W3	W4 V4	
Check I/E criteria (MD)	xBC	xCVD								(16 to 18	(x)	xCVD								REDCap Form 3
Intro to study (RA)	xBC	xCVD								months)	(x)									SIP (Annex 2)
Sign Informed consent	xBC	xCVD									(x)									On paper
Sign HDI agreement	xBC	xCVD									(x)									On paper
Create HDI account (through AIDAVA)	xBC	xCVD									(x)									
Data extract Hosp/HDI	xBC	xCVD																		After signing ICF
Training the research team	x																			Hospital contact persons, RA, expert curator, MD
Training - on site		x										x								
Training - on line					х										х					
User profile - Health and digital literacy		х										x								REDCap Form 1 (Patient, Curator)
Site monitoring forms		x	x	x	x	x	x	x	x			x	x	x	x	x	x			REDCap Forms 4,5,6,7 (RA)
System Usability Scale							x										x			REDCap Form 8 (Patient, Curator)
Fill in QALY		x										x								Personal Apps
Use BPM device		xCVD	xCVD		xCVD	xCVD				xCVD	xCVD	xCVD		xCVD	xCVD					See Section 6.2

		Intervention Period Weeks (with a washout of 16 to 18 months)															Notes			
	Screen				Gener	ation	1				Rescreen									
Procedure	before W1)	W1 D1 V1	W1	W1 D5	W2 D1 V2	W2	W2 D5 V3	W3	W4 V4	Develop G2	(< 15 d before W1)	W1 D1 V1	W1	W1 D5	W2 D1 V2	W2	W2 D5 V3	W3	W4 V4	
Curate data with AIDAVA		x	x	x	x	x	x					x	x	x	x	x	x			
Curator form - patient							x										x			REDCap Form 11 (Patient)
Curator form - expert	G0						x										x			REDCap Form 9, 10 (Curator)
IPS extract				x			x							x			х			
Extract BC registry				xBC			xBC							xBC			xBC			
Query Federated BC reg. /sec. endpoints				хBС				хBС						хBС				хBС		
SMART risk score (CVD)				xCVD			xCVD							xCVD			xCVD			Manual & auto
Data user form: BC, CVD							x										x			REDCap Form 12,13 (BC), and 14 (CVD)
Feedback to Patient (results + regular info)									x	every 3 mth									x	
Confirm delete data (if dropping out)									x										x	

Figure 2. Schedule of Activities

x = all patients

(x) = only for patients who did not participate to G1 evaluation

xBC = Breast Cancer patient only

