The senior physician will then be able to decide on one of the following reasons for discrepancy. Health record incomplete: the information was not available in the medical record, while it should have been – and therefore AIDAVA could not identify the right value.

- Error in AIDAVA: the information is rightly included in the medical record, but AIDAVA did not include this information properly
- Error from physician: AIDAVA is right and the junior physician evaluation is not correct.

To assess the longitudinal aspects of AIDAVA, the SMART score will be calculated 2 times (after G1 and \pm 16 to 18 months later, at the end of G2 use year follow-up). The aim is to see if modifiable risk factors can be captured and risk can be calculated by AIDAVA automatically and reliably.

4. Study Design

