G1 and G2 VISIT 1 - on site W1 Day 1 (either elective outpatient clinic visit OR inpatient stay during index MI event),	 Approximately up to 50 inpatients screened, 15 inpatients enrolled (Note: Day1 and Day2 may seem busy for a patient recovering from MI; most patients are however recovering well and find difficult to remain in hospital during the monitoring period) 1. Checking I/E criteria (In REDcap) 2. Project introduction (10 min, doctor). Research associate complete REDCap Form (in REDCap, Patient Screening FORM) If the patient meets the criteria and is interested in participating in the project, he/she will move on to the research associate 3. Under supervision of Research Associate - 30-60 min per patient 	

	CVD patients	BC patients
	 a. Share details of the project with patients ; b. Provision of SIP and explanation - including use of EQ-5D QALY - quality of life questionnaire several time c. Introduction of HDI and questions regarding ownership and future use of the data through HDI d. Answer to questions e. Request to read and sign ICF and HDI agreement f. Provide medical device to patient 4. Research associate update REDCap Form (in REDCap, Patient Screening FORM) 5. Confirmation of patient enrollment; 	
	 Create HDI account (through AIDAVA) Questionnaire to specify user profile (In REDCap 3. Training session for the patient on the prototyp Patient fills EQ-5D form through HDI provided a Research associate complete REDCap Form (sources for enrolled patients Patient and expert curator curate medical data), User Profile FORM) e by the research associate pp in REDCap, Patient monitoring FORM) data extraction from different with AIDAVA
W1	CVD patient will use medical device	
Day 2 - 5	 Patient will use AIDAVA and test its functionalities, take notes and if necessary, will contact Helpdesk whenever needed Expert curator will curate the data in AIDAVA on demand. RA fill the patient monitoring form (in REDCap, Patient monitoring FORM) 	
W1 Day 5	 First calculation of SMART risk score by AIDAVA (automatically) and CVD expert (manually). Data collection and entry forms : Documentation of SMART risk score calculation result and time (in REDcap, Patient Monitoring FORM) by RA 	 System extracts the patient data for insertion into the local AIDAVA BC registry Queries identified as secondary end points will be fired automatically by the system and results available for display to the BC data users

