	1. Data curators spreadsheet (Patient as curator and Exper Form)	t Curator), (in REDCap, Patient Curator FORM; Expert Data Curator

	CVD patients	BC patients
	 Data user/consumers spreadsheet (In REDCap Data use AIDAVA extract IPS and forward it automatically to the H monitoring FORM) 	r/consumer FORM) IDI + enter flag in Data collection and entry forms (REDCap, Patient
VISIT 2 - online W2 Day 1	CVD patients use medical device Check if there is any issue with the medical device (CVD patient only)	
	 Second training session on the prototype - online (open Patient and expert curator curate medical data using All RA fill the patient monitoring form (in REDCap, Patient in Complexity) 	questions) DAVA monitoring FORM)
W2 CVD patient will use medical device		
Day 2-5	 Patient will use AIDAVA and test its functionalities, take Expert curator will curate the data in AIDAVA on deman RA fill the patient monitoring form (in REDCap, Patient in AIDAVA) 	notes and if necessary, will contact helpdesk d. monitoring FORM)
VISIT 3 W2 Day 5	 Second calculation of SMART risk score by AIDAVA and CVD expert Data collection and entry forms: documentation of SMART risk score calculation result and time 	
	 AIDAVA extract IPS and forward it automatically to the HDI (+ enter flag in REDCap, Patient monitoring FORM) Patient and curator will fill in the system usability scale questionnaire online (in REDCap, System Usability Scale - SUS FORM) Data curators spreadsheet (Patient and Expert Curator). (in REDCap, Patient Curator FORM; Expert Data Curator Form) Data user/consumers spreadsheet (In REDCap Data user/consumer FORM) 	
W3		At the end of G1 - across all sites - fires the queries identified as secondary end points; RA reports the results in the data users/consumers spreadsheet (in REDCap Data user/consumer FORM).
End of evaluation	Delete personal patient data and PHKG (after finalisation of evaluation report), but keep evaluation score from G1.	
VISIT 4 - online W4	Feedback to patient	

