Training session for the patient on the prototype done?	 ⊕ ○ Yes ⇒ ○ No 			
Comments:	(free text)			
VISIT 1 (Week 1/Day 5) - Data extraction / calculation (the form	is filled by research associate)			
Date:	H Today Y-M-D			
Data curation (Week 1) by patient done?	 ⊢ ○ Yes ○ No 			
Data curation (Week 1) by expert curator done?	 ⊕ ○ Yes ⇒ ○ No 			
Did the patient check their International Patient Summary extract (transferred to HDI automatically)?	 ⊢ ○ Yes ○ No 			
Automatic extraction BC registry, query done (BC patients) an viewed by BC specialists?	d ⊕ ○Yes			
Comments:	(free text)			

For BC patients

VISIT 1 (Week 1/Day 5) - Data extraction / calculation (the form	m is filled by research associate)	
Date:	H Today Y-M-D	
Data curation (Week 1) by patient done?	 ⊢ O Yes ⊃ O No 	reset
Data curation (Week 1) by expert curator done?	 ⊕ O Yes ⇒ O No 	reset
How many times did you check your blood pressure with the BPM during the last week (expected to be a minimum of 3 times during the week, 3 times a day)?	(e.g. 2 or 3 how many times during the week) (e.g. frequency of each measurement)	
Did the patient check their International Patient Summary extract (transferred to HDI automatically)?	⊢ O Yes ⊖ O No	reset
SMART score (CVD patients) available and - viewed by CVD specialists - calculated by system	⊢ O Yes ⊖ O No	reset
Comments:	(free text)	

For CVD patients

Online training for patient (Week 2/Day 1)		
Date:	H Today Y-M-D	
Online training for patient done?	 ⊢ ○ Yes ⊃ No 	reset
Comments:	(free text)	

Online training for patient (Week 2/Day 1)					
Date:	H C Today Y-M-D				
Online training for patient done?	 (⊢) ○ Yes (○) No reset 				
Check any issue with medical devices (CVD patient only)	Issue:				
	(free text)				
	Proposal for resolution:				
	(free text)				
In case of change of medical device:	ID of old device:				
(CVD patient only)					
	Issue with old device:				
	(free text)				
	ID of new device:				
	Date of change: Today Y-M-D				
Comments:					
	(free text)				

For CVD patients

Visit 3 - Data extraction / calculation (Week 2/Day 5) (the form is filled by research associate)				
Date:	H Today Y-M-D			
Data curation (Week 2) by patient done?				
Data curation (Week 2) by expert curator done?				
Automatic extraction BC registry, query done (BC patients on and viewed by BC specialists?	ly) R ○ Yes			
Patient Curator form	Incomplete			
Expert Data Curator Form	Complete			
Data user/consumer (Breast Cancer Specialist) Form	Complete			

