10.3.4 Data user/consumers spreadsheet: Breast Cancer Specialist and CVD clinicians

Breast Cancer

Form to be used by the Breast Cancer Specialist to enter time related to management of the BC registry

Breast Cancer Specialist - Data User Form - G0	
Site name:	 NEMC - Sihtasutus Põhja-Eesti Regionaalhaigla UM - Maastricht University MUG - Medizinische Universität Graz
Data User ID / pseudonym:	✓
To be computed for 45 patients across sites (15 patients in your own site + time to get info on 30 patients in t	he other 2 sites)
TBC1. Estimated time to compute the percentage of patients - across sites - treated with breast conserving therapy and whole breast radiotherapy that receive a boost to the tumour bed without AIDAVA (in min):	(example: 2 or 6 or)
TBC2. Estimated time to compute the number of patients - across sites - undergoing surgery and radiotherapy, without adjuvant chemotherapy: % of patients with time between surgery and radiotherapy > 8 weeks without AIDAVA (in min):	(example: 2 or 6 or)
TBC3. Estimated time to compute the number of patients - across sites - receiving radiotherapy: Percentage of patients receiving any nodal radiotherapy without AIDAVA (in min):	(example: 2 or 6 or)

This form is linked with a table that contains all the metrics manually entered in REDCap (as .csv-export) that are needed to evaluate the system from a BC specialist perspective.

Breast			G1				G2	
Cancer	BC1	BC2	BC3	Comments	BC1	BC2	BC3	Comments
NEMC								
MUG								
Maastro								
MEAN								
MEDIAN								

CVD specialist

Form to be used by the CVD specialist to enter the manually computed SMArt score and the time needed to compute this form manually

CVD Specialist - Data User Form - G1 & G2	
Generation of the prototype	 B O Generation 1 C Generation 2 reset
Site name:	 NEMC - Sihtasutus Põhja-Eesti Regionaalhaigla UM - Maastricht University MUG - Medizinische Universität Graz
Data User ID / pseudonym:	~
Patient ID / pseudonym:	
Date:	H Today Y-M-D
CVD1. SMART risk score computed by the physician(s) for the patient (from this site): U-prevent SMART risk score calculator	SMART risk score computed by CVD Specialist SMART risk score computed by another person Name of this other person
TCVD1. Time required for the treating physician to compute the SMART risk score (collect + analyze + enter data into a standalone web page calculator) in min:	(example: 10 or 20 or)

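### The protocol conflicts on when the manual SMART score and time are recorded, and does not say which of two scorings per generation supplies the cardiovascular endpoints

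*Protocol*

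**What the plan says.** Five places in the protocol bear on when the SMART score is calculated and recorded.

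- **Section 3.2.2** introduces the longitudinal aim and says that "the SMART score will be calculated 2 times": after G1, and 16 to 18 months later at the end of G2.
- **Section 4.4.2, W1 Day 5** has "First calculation of SMART risk score by AIDAVA (automatically) and CVD expert (manually"). It asks for "Documentation of SMART risk score calculation result and time (in REDcap, Patient Monitoring FORM) by RA", and the same block lists "Data user/consumers spreadsheet (In REDCap Data use"r form).
- **Section 4.4.2, Visit 3 (W2 Day 5)** has "Second calculation of SMART risk score by AIDAVA and CVD expert", with result and time documented again and the data user form listed again. Section 4.4.4 repeats both blocks for returning patients in G2.
- **Section 1.3 (Schedule of Activities)** marks the SMART row, annotated as manual and automatic, at W1 D5 and W2 D5 in both generations. The data user form row, annotated "REDCap Form 12,13 (BC), and 14 (CVD"), is marked at W2 D5 only.
- **Section 10.3** prints the forms. Form 14 carries the manual score (CVD1) and "TCVD1. Time required for the treating physician to compute the SMART risk score", plus a date. The patient monitoring form for W1 Day 5 carries "SMART score (CVD patients) available and - viewed by CVD specialists - calculated by system" as a yes/no item, with no field for a score or for minutes.

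Sections 9.2 and 9.3 use the manual time and the accuracy once per generation and do not name the occasion.

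**The concern.** Cardiovascular Metric 1 compares the physician's time to collect, analyse and enter the inputs with AIDAVA's automatic calculation. Metric 2 compares AIDAVA's score with the physician's. Both need a manual value that represents ordinary practice and was formed independently of AIDAVA.

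A second manual scoring of the same patient a week later may be neither. Some inputs have already been collected, which would shorten the time. AIDAVA's week-1 score has also been available to CVD specialists, which could draw the manual score towards it. The first effect works against AIDAVA on time; the second works in its favour on agreement, for which section 9.1 sets a threshold of 80% or more.

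There is also a comparability problem. A site that follows section 4.4 may file Form 14 at W1 D5, at W2 D5 or at both. A site that follows the schedule files it at W2 D5 only. All of these values would enter the same cross-site mean and median in the section 10.3.4 table.

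**Working it through.** **Step 1: count the calculations.** The schedule and section 4.4 give 2 per generation. Over 2 generations, 2 × 2 = 4 per patient who takes part in both. Section 3.2.2 names 2 time points. Section 9.4 gives 45 CVD patients (15 at each of 3 sites). If all 45 took part in both generations, the manual scores would number 45 × 4 = 180, against 45 × 2 = 90 with one per generation. Per site and generation this is 15 × 2 = 30 against 15.

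**Step 2: interval.** W1 D5 to W2 D5 is (7 + 5) − 5 = 7 days.

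**Step 3: set recording against calculation, within one generation.**

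| Occasion | Manual scoring | Form 14 in 1.3 | Data user form in 4.4 | Field in monitoring form |
|---|---|---|---|---|
| W1 D5 | yes | no | yes | yes/no item only |
| W2 D5 | yes | yes | yes | yes/no item only |

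The first manual time is therefore requested in 4.4, but the monitoring form named for it cannot hold it. Whether Form 14 is open that day depends on which section the site follows.

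**Step 4: does the second scoring come after AIDAVA's first?** Yes. The automatic score is produced at W1 D5, and that day's monitoring form asks whether CVD specialists viewed it.

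**Step 5: is it the same scorer?** No section says so. TCVD is defined for the treating physician, and the site form in 10.3.2 has places for two CVD specialists, which makes a repeat by one person likely. Form 14 also allows a score by another person.

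**Step 6: what a repeat would do to the time.** The documents give no figure, so this is illustration only. Let *r* be the repeat time divided by the first time. Manual time is understated by 1 − *r*:

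- *r* = 1.00: 0%
- *r* = 0.90: 10%
- *r* = 0.75: 25%
- *r* = 0.50: 50%

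**Step 7: effect on the G1 minus G2 time contrast in section 9.3.** If the repeat saves the same number of minutes *c* in each generation, (T1 − *c*) − (T2 − *c*) = T1 − T2, so the effect cancels. If it saves the same proportion, *r*T1 − *r*T2 = *r*(T1 − T2): the contrast shrinks but keeps its sign. The exposure lies mainly in the manual-versus-AIDAVA comparison. The cancellation also requires the same occasion to be used in both generations.

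**The case against.** The strongest case on the other side is that this is a mismatch of form timing and little more.

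- **The first time is planned to be captured.** Section 4.4 asks for result and time at W1 D5 and lists the data user form there, and the schedule's heading points to Section 4 for detail. This stands. A reader might infer that the recorded manual time is necessarily a practised repeat; the documents do not support that. It is what follows if the schedule governs. Section 8 does give the schedule force by requiring adherence and allowing no waivers.
- **Section 3.2.2 need not be a cap.** A reader might infer that it permits only one calculation per generation. Its sentence opens with the longitudinal aim and can be read as naming two time points without limiting the calculations inside each. The counts of 180 and 90 describe workload under the two readings; they do not prove an error.
- **The same physician is not stated.** This stands, so any practice effect is conditional. Manual time is also the user's own estimate, which makes a mechanical saving on repetition less certain.
- **The inference is little affected.** The hypothesis in 9.1 is that CVD specialists spend no time at all, and the G1–G2 contrast is largely protected. Both are fair points, but neither covers the manual-versus-AIDAVA time or the independence of the reference score.
- **The senior physician sees AIDAVA's parameters by design.** True, but that is a check made after the treating physician has scored. It does not make prior sight of AIDAVA's score harmless to the treating physician's own value.
- **The analysis plan can choose the occasion.** Form 14 is dated, so two entries could be told apart. A later choice cannot recover a first value that was never entered.
- **The curator forms show the same drift,** and scoring after each week of curation has a plausible purpose. Both are true, and the second is a reason to allow the week-1 scoring to stay.

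**Conclusion.** The point holds as an internal conflict that should be corrected. Sections 1.3, 4.4 and 10.3 disagree on when and where the manual SMART score and time are recorded. Section 3.2.2 names fewer time points than the visit tables schedule. No section says which occasion supplies TCVD and CVD1.

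If the schedule is followed, the endpoint values come from a second scoring of the same record 7 days after the first, with AIDAVA's week-1 score already available to CVD specialists. If the same physician also scores both times, manual time may be too short, which understates AIDAVA's saving, and agreement may be too high, which favours AIDAVA. The size of either effect is unknown: the 0% to 50% range for time rests on assumed ratios, and no range can be given for agreement.

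**What to change.** Reconcile sections 1.3, 3.2.2, 4.4 and 10.3. State that TCVD1 and CVD1 are the treating physician's first manual calculation for that patient in each generation, entered in Form 14 before AIDAVA's score is shown to that physician. Either of two arrangements achieves this:

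1. **Keep both manual calculations.** Place Form 14 at W1 D5 for the first one and define the endpoints from that entry. Correct the reference to the monitoring form, or give that form fields for score and minutes. The cost is a small change in form timing.
2. **Keep one manual calculation, at W2 D5.** Remove the W1 D5 manual calculation from 1.3, 4.4.2 and 4.4.4, and keep the automatic W1 D5 score as a system check not shown to the scorer. This halves the manual scoring, from 30 to 15 per site and generation. The cost is the loss of the week-1 manual comparison.

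Under either arrangement, section 3.2.2 should state how many calculations are made in each generation, and section 9.2 should name the occasion used.

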4.1 Overall Design

The assessment study will be a cohort, 3 arms, prospective¹³ study involving 30 patients (15 breast cancer and 15 CVD) + 3 expert curators in each site. It will be based essentially on available data, collected during clinical care (see Section 10.1 for detailed description of data sources), but will also include some prospective data from medical devices and Quality of Life questionnaire

There will be 3 arms that will allow comparison across these different populations of users.

- "G1 and G2" patients who contributed to evaluation of G1 and G2.
- "Single Generation" patients who contribute to the evaluation of only one generation of the prototype (G1 or G2)
- Expert data curators

There will be 4 epochs

- Epoch 1 will last 1 week and take place just before deployment and evaluation of G1; it will allow to gather information from the expert curator on the current situation/curation process and to provide a dedicated training to the curators.
- Epoch 2 will last for 2 weeks, and is expected to take place in the period of July September 2024. Patients will be requested to ingest their data with the support of the prototype, and to curate them. Whenever needed, the data expert curator will be able to support them.
- Epoch 3 will last for 16 to 18 months: "wash out" period during which G2 of the prototype will be developed;
- Epoch 4 will last for 2 weeks and is expected to take place in the period February/March 26. Patients and curators will be requested to assess Generation 2 (G2) of the prototype, by performing the same task as in Epoch 2 to enable comparison of the performance of the 2 generations of the prototype.

4.2. Patient input in Study Design

The development of the AIDAVA prototype is taking place with the support of "patient consultants" selected by the ECPC (European Patient Cancer Coalition) and EHN (European Heart Network) patients associations. The selected patient consultants are people with a genuine interest in being more in control of their own medical record (or the health record of their loved ones) to improve the quality of their own health and support clinical research; during the AIDAVA project, they do not contribute their personal data but act as representatives of patients.

Four patient consultants were selected from each organisation; each patient consultant is supporting the project for about 42 person days - including participation in co-creation workshops - and is paid for this effort as consultant based on a fee (350 EUR/day) recommended by the European Patient Forum at the time of writing the proposal.

One of the tasks of these patient consultants was to review the enclosed protocol; they also will be asked to review interim versions of the prototype in development and to pre-test the AIDAVA prototype.

¹³ This is a prospective study as we enrol patients, check existing data and collect new data (QALY and medical device data) and see how the endpoints develop. A portion of the study is however retrospective as we use existing data available within the medical dossier of a patient.

